# Memorial Sloan-Kettering Cancer Center IRB Protocol

IRB#: 09-159A(10)

## Memorial Sloan-Kettering Cancer Center IRB Protocol

IRB#: 09-159A(10)

### 1.0 PROTOCOL SUMMARY AND/OR SCHEMA

This phase II study of the anti-GD2 murine IgG3 monoclonal antibody 3F8 combined with granulocyte-macrophage colony stimulating factor (GM-CSF) will assess relapse-free survival in patients who are in first complete/very good partial remission (CR/VGPR) but are at very high risk of relapse of neuroblastoma. The high-dose 3F8 usage is four fold greater than the standard 3F8 dosage used in prior phase II studies. 13-*cis*-Retinoic Acid will be used in this protocol after patients are evaluated for response to 3F8/GM-CSF. We will apply real-time quantitative RT-PCR methodology targeting GD2 synthase mRNA for monitoring response in bone marrow; we will test the hypothesis that early bone marrow response has prognostic importance.

### 2.0 OBJECTIVES AND SCIENTIFIC AIMS

#### Primary Objectives

- Assess the impact of high-dose 3F8/GM-CSF on relapse-free survival in patients in first complete or very good partial remission, but at high risk of relapse.

#### Secondary Objectives

- Apply real-time quantitative RT-PCR to test the hypothesis that the minimal residual disease content of bone marrow after the first treatments with 3F8/GM-CSF has significant prognostic impact on relapse-free survival.
- Monitor safety of the high-dose antibody treatment, to assure no side-effects or noxious sequelae develop or emerge that were not seen in the prior phase I study.

### 3.0 BACKGROUND AND RATIONALE

**3.1 Disease background:** Neuroblastoma (NB) is the most common extracranial solid tumor of childhood; 50-60% of patients present with an unresectable primary tumor and metastases in bone marrow (BM). Intensive induction chemotherapy and aggressive surgery have improved remission rates in young patients; results have been less impressive in adolescents and adults in whom NB is especially chemoresistant. Realization of an effective strategy for eradicating minimal residual disease (MRD) has remained a formidable challenge. Post-surgical use of local radiotherapy helps control MRD in the primary site. Myeloablative therapy (with stem-cell support) has been the most common approach for eradicating MRD in distant sites. The long-term relapse-free survival rate in a recent national study was only ~20%, although the vitamin A derivative 13-*cis*-retinoic acid helped to improve overall survival. These results, plus the potentially severe toxicities of chemotherapy and radiotherapy, are compelling reasons for pursuing novel therapeutic approaches, including immunotherapy mediated by anti-GD2 monoclonal antibodies (MoAbs) which interact with granulocytes.

Amended: 02/24/15

## Memorial Sloan-Kettering Cancer Center IRB Protocol

IRB#: 09-159A(10)

**3.2 Rationale for 3F8:** 3F8 is a murine IgG3 MoAb that is well suited for targeted immunotherapy. The reasons are several. First, the intensive chemotherapy required to produce in NB patients the minimal disease state optimal for immunotherapy results in prolonged lymphopenia. This setting is unfavorable for active immunotherapy but allows passive immunotherapy since the patient is unable to reject allogeneic, xenogeneic, or genetically-engineered MoAbs. Second, 3F8 recognizes the ganglioside  $G_{D2}$ . This target antigen is highly expressed on NB (but has restricted distribution in normal human tissues), is not modulated from the cell surface when bound by MoAbs, and is genetically stable (unlike tumor-associated antigens such as immunoglobulin idiotypes on lymphoma cells). Third, scintigraphy using  $^{131}I$ -3F8 confirms that 3F8 localizes selectively to  $G_{D2}(+)$  tumor deposits in patients. The excellent targeting potential of 3F8 was evidenced by its high tumor to non-tumor ratio, the high percent injected dose per gram uptake, and the limited, if any, nonspecific liver and spleen uptake. Fourth, 3F8 mediates destruction *in vitro*, in a dose-dependent manner, of  $G_{D2}(+)$  human tumor cells by human complement and by human lymphocytes, cultured monocytes, and neutrophils. Finally, the capacity of 3F8 to activate complement (C') on NB cells (which lack decay accelerating factor) raises the possibility of C'-mediated lysis in patients and the release of C' fragments that may elicit an inflammatory influx of granulocytes capable of lysing 3F8-labeled tumor cells. Furthermore, the deposition of C' fragments C3b and iC3b on NB cells may enhance ADCC because the receptor for iC3b – variously called Mac-1, CR3, CD11b/CD18, or  $\alpha_M\beta_2$ -integrin – is a key element in anti- $G_{D2}$  MoAb-mediated tumor-cell kill by neutrophils, which are the most abundant circulating class of leukocyte.

**3.3 Rationale for GM-CSF:** GM-CSF can amplify 3F8 anti-NB activity in patients via effects on granulocytes and macrophages. Reasons for combining GM-CSF with 3F8 include the following. First, granulocyte production is only transiently suppressed by chemotherapy, and GM-CSF increases neutrophil and eosinophil production and is well tolerated compared to other cytokines such as interleukin-2. Second, granulocytes from patients receiving chemotherapy and normal volunteers mount ADCC against NB cells via non-oxidative mechanisms, and GM-CSF enhances the ADCC. Third, eosinophilic infiltration of some cancers has favorable prognostic significance, and eosinophils exhibit potent antitumor activity in animal models. Fourth, activated monocytes-macrophages efficiently phagocytose NB cells, and exposure *in vitro* or *in vivo* to GM-CSF primes monocytes-macrophages for greater antineoplastic cytotoxicity. Fifth, GM-CSF enhances the proliferation, maturation, and function of antigen-presenting cells, including antigen processing and presentation by macrophages and dendritic cells - effects that might promote induction, or antitumor activity, of an idiotypic network. Finally, GM-CSF is not a growth factor for NB cells *in vitro*.

Amended: 02/24/15

## Memorial Sloan-Kettering Cancer Center IRB Protocol

IRB#: 09-159A(10)

**3.4 Rationale for quantitating BM disease by real-time RT-PCR:** Curative strategies for stage 4 NB must encompass control of both the primary mass and distant disease. Dose-intensive chemotherapy has had a favorable impact on resectability of primary tumors and surgical removal of all visible tumor, followed by local radiotherapy, reduces the risk of relapse in the primary site to <10%. Dose-intensive chemotherapy eliminates histologically evident BM involvement in 90% of high-risk cases. These encouraging results have shifted the focus of curative strategies to the problem of MRD – which is readily assessed in BM.

Adjuvant treatments, such as immunotherapy with MoAbs, may make gradual and not quantum changes in MRD, which by definition is beyond the sensitivity of conventional histologic or radiologic techniques. The availability of more sensitive methods for quantitating occult tumor cells in sequential BM specimens can allow determination of the efficacy and optimal duration of adjuvant treatment. The absence of detectable tumor cells in BM can serve as a surrogate end point for the adjuvant treatment strategy, while quantitative data on BM disease will help detect relapse earlier and indicate a need for a change in treatment.

We58-65a and others have reported a series of studies aimed at improving the utility of BM testing, focusing on immunological and molecular methods for identifying MRD. The limit of detection for immunocytology is 1/10^5 to 1/10^6 cells; RT-PCR has slightly superior sensitivity with a range of 1/10^5 to 1/10^7 cells. *The results suggest that GD2 synthase might serve as a sensitive marker of MRD in BM and that its level might reflect clinical disease status as well as correlate with histologic response to immunotherapy.*

Histologic examination of aspirates and biopsies from bilateral posterior iliac crests has been the standard method for detecting NB in BM. We have routinely also obtained specimens from bilateral anterior iliac crests since sampling from multiple sites increases detection rates.65a Histologic studies alone, however, yield an underestimate of BM involvement, as shown by immunocytology with MoAbs. For >15 years, we have used anti-GD2 immunocytology to enumerate NB cells in BM of patients. Molecular markers have also been tested for detecting NB. Thus, the gene transcript for tyrosine hydroxylase, which is a key enzyme in the catecholamine biosynthesis pathway, is useful for identifying NB in BM but its expression is down-regulated in some cells. We found cancer-testis antigen *GAGE* to be comparable in sensitivity to immunocytology in detecting NB in BM and results with *GAGE* proved to have prognostic significance.

Ease of use, superior sensitivity, and greater specificity prompted us to study the utility of real-time quantitative RT-PCR of GD2 synthase mRNA for the detection of rare NB cells in BM. The marker GD2 synthase is particularly pertinent because NB cells express ganglioside GD2 at high density, with little heterogeneity within tumors or among patients, and this surface antigen has limited expression in normal human tissues. The key enzyme required for GD2 synthesis is GD2 synthase ( $\beta$ 1,4-N-acetylgalactosaminyltransferase, EC 2.4.1.92).

Amended: 02/24/15

## Memorial Sloan-Kettering Cancer Center IRB Protocol

[figure not shown]
IRB#: 09-159A(10)

In a study of 155 BM samples (100 patients), the transcript levels correlated well with the number of NB cells in BM as measured by immunocytology. Further, in a study of BM findings in 86 NB patients treated with 3F8 and GM-CSF, molecular responders had a significantly lower risk of disease progression. The data provide compelling support for the utility of this molecular approach for assessing MRD.

**3.5 Clinical experience with 3F8/GM-CSF:** Prior clinical studies of 3F8/GM-CSF established 1) this combination's excellent activity against refractory BM disease (IRB protocols 94-018 and 03-077); 2) the safety of markedly augmented 3F8 dosing (IRB protocol 05-015: "3F8 antibody dose escalation plus granulocyte-macrophage colony-stimulating factor in high-risk neuroblastoma: A phase I trial")71a compared to dosages derived from pilot studies in the 1980s, an important finding since *in vitro* studies show a 3F8 dose-dependent lysis of NB cells (see section 3.2); and 3) the superiority of subcutaneous over intravenous (iv) use of GM-CSF, for both anti-NB effect and treatment simplification (which helps patients and medical staff - and promotes wide availability of this treatment)

The long-standing standard daily dosage of 3F8 has been 20 mg/m^2. In the IRB protocol 05-015 dose escalation phase I study, 3F8 dosages up to 160 mg/m^2 were possible without dose-limiting toxicity, as reported71a (That protocol also used a small dose of heat-modified 3F8 – 2 mg/m^2, iv over ~5 minutes – administered just before the treatment dose, as a way to modify the major acute toxicity of pain.) For the current protocol, we chose daily 3F8 dosage 80 mg/m^2 because in the dose escalation phase I study, serum levels were not significantly different at a 3F8 daily dosage of  $\geq$ 80 mg/m^2 (see Figure 1), and excellent anti-NB activity was seen at 80 mg/m^2.

Figure 1:

Amended: 02/24/15

## Memorial Sloan-Kettering Cancer Center IRB Protocol

IRB#: 09-159A(10)

**3.6 HAMA response/idiotypic network:** In a study of 34 patients with MRD treated with 3F8 alone, patients with a self-limited (transient) HAMA response had significantly better PFS than patients who had persistently high HAMA titers or no HAMA formation. This association of a transient low level HAMA/anti-idiotype (Ab2) antibody response with better PFS was a seemingly paradoxical finding since HAMA/Ab2 blocks 3F8 binding to tumor cells. The unexpected observation regarding HAMA/Ab2 and survival led to the hypothesis of a host idiotypic network induced by 3F8 (Ab1) and responsible for long-term tumor control. The idiotypic network was first postulated by Jerne for immune regulation and later demonstrated in human disease models, including cancer patients. Anti-idiotypic antibodies (Ab2) in the HAMA pool may mimic antigen GD2 and stimulate an Ab3 antibody response. We previously reported the association of anti-anti-idiotype (Ab3) with prolonged survival among patients who underwent myeloablative therapy with autologous stem-cell rescue. Other investigators have postulated the development of an idiotypic network in patients treated with 17-1A antibodies, where both Ab3 antibodies as well as anti-idiotypic and anti-anti-idiotypic T cells have been demonstrated.

In our study of 34 patients, consistent with the emergence of an idiotypic network, Ab3 (anti-anti-idiotype) and Ab3' (anti-GD2) response at 6-14 months after treatment with 3F8 alone correlated with improved PFS, and higher Ab3 titers showed a stronger correlation with improved outcome, while non-idiotype antibody responses (anti-mouse or anti-tumor nuclear antigen) had no apparent impact on outcome. Since GD2 is an auto-antigen, induced Ab3' response represented a breakdown in self-tolerance. We hypothesized that significant rises in Ab3 or Ab3' would not be possible unless suppressor pathways were removed and naive T or B cells were allowed to repopulate. Following intensive chemotherapy that eliminates a large part of the lymphoid system, exposure to tumor-selective Ab1s (3F8) might induce unique Ab2s that could bias the recovering repertoire towards the GD2 antigen network. The potential for biasing the immune system towards specific antigens has been well documented in murine models and human disease states. If true, one would expect such an idiotypic network to be most successful following intensive immunosuppressive therapy, and not easily induced in immunocompetent patients. In fact, we found that myeloablative therapy suppressed HAMA and Ab2 but was followed by the appearance of Ab3 which in turn correlated with prolonged survival. The prerequisite of strongly immunosuppressive therapy may explain why in most clinical studies of MoAbs, such an idiotypic network is not commonly observed. However, when found in patients with colorectal or ovarian carcinoma treated with specific MoAbs, the idiotypic network gave patients superior survival advantage.

Amended: 02/24/15

## Memorial Sloan-Kettering Cancer Center IRB Protocol

IRB#: 09-159A(10)

**3.7 Isotretinoin (13-cis-retinoic acid)** was shown in a randomized national study to significantly decrease the risk of early relapse in patients treated in complete remission and to significantly improve overall survival. This agent subsequently became standard of care for NB patients in remission. It will be used in this protocol after patients are evaluated for response to 3F8/GM-CSF – same dosage, same timing as in the predecessor 3F8/GM-CSF (IRB 03-077) protocol.

**3.8 Interpretations and implications:** Various strategies have undergone clinical testing to promote immune-mediated attack against cancer. However, few clinical trials have used MoAb-targeted immunotherapy against solid tumors in children or adults, especially with ADCC as the principal underlying immune cytotoxic mechanism. Also, an antineoplastic role for granulocytes has received scant attention. A treatment program combining 3F8 and GM-CSF thus represents a step towards filling a gap in the emerging field of immunotherapy.

This phase II trial exploits recent findings that promise to optimize the anti-NB activity of 3F8/GM-CSF – namely, high dosing of 3F8 and subcutaneous use of GM-CSF. Further, RT-PCR analysis of response in BM, which has proved informative in past studies, will be applied to monitor anti-NB activity of the immunotherapy, with an emphasis on early recognition of treatment efficacy. The studies focus on BM; findings may not reflect total body tumor burden. Metastatic NB is, however, a systemic disease, and, as with leukemia, BM status appears to approximate the overall disease state. If the RT-PCR method proves to be sensitive, it will provide a useful tool for measuring NB-cell content in BM as a patient goes through treatment. The ability to identify patients not likely to benefit from further use of a given adjuvant therapy will allow a more timely switch to a possibly better treatment. We hypothesize that quantifying GD2 synthase transcript levels will help stratify patients by tumor load, define tumor thresholds that correlate with favorable clinical outcome, and provide prognostic classification for patients receiving immunotherapy. Risk-related molecular guidelines can be rapidly incorporated into future treatment programs.

Our RT-PCR method provides a quantitative measure, such that the percentage of patients who achieve CR in BM, and the degree of response with 3F8/GM-CSF, can be calculated and compared to other adjuvant treatments. With NB, where randomized trials are difficult to carry out because of the small number of affected patients, such quantitative analyses acquire even greater utility for rapidly identifying both the best agent and its optimal use in a curative treatment program.

The findings regarding RT-PCR utility in the adjuvant setting, granulocyte activation, and idiotypic network will have general implications for MoAb-based therapeutic strategies against solid tumors in humans.

Amended: 02/24/15

## Memorial Sloan-Kettering Cancer Center IRB Protocol

IRB#: 09-159A(10)

The ease of administration of the treatments (a subcutaneous injection of GM-CSF, which is given at home, and a 30-minute iv infusion of 3F8 in the outpatient clinic), plus their transient acute side-effects, are compatible with usage of this regimen beyond our hospital – a strong positive factor in furthering product development, which in fact is underway in a multi-institutional study of 3F8/GM-CSF using the previous 3F8 dosage.

### 4.0 OVERVIEW OF STUDY DESIGN/INTERVENTION

#### 4.1 Design

This phase II, open-label, single arm trial assesses the anti-NB activity of high-dose 3F8 (80 mg/m^2/day), which is used in cycles 1-2, with return to standard 3F8 dosage (20 mg/m^2/day) in subsequent cycles. Clinical results will be compared to those in the predecessor trials which used only the standard 3F8 dosage.

Starting with A(8), patients no longer receive high dose 3F8 but receive only standard dose 3F8 (20mg/m^2/day) for all cycles.

The patients are in 1st complete/very good partial remission (CR/VGPR) after conventional therapy, with no evidence of NB by standard studies, but are at high risk for relapse.

Real-time quantitative RT-PCR will be used to assess MRD in BM. 13-*cis*-retinoic acid is started after cycle 2.

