## Memorial Sloan-Kettering Cancer Center IRB Protocol

IRB#: 09-159A(10)

a full 5-day cycle. GM-CSF will be continued through the 3F8 make-up day at the 500 mcg/m^2 dose.

\*High-dose 3F8 will be administered only for patients enrolled on protocol from A(0) to A(7). Starting with A(8), patients receive standard dose (20mg/m^2/day) during cycles 1 and 2.

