#### 14.2 Sample Size

We will use a Simon's two-stage design. The type I error rate is set as 0.1 and the type II error rate as 0.1.

In the predecessor trial (IRB 03-077: 3F8 at standard dosage of  $100 \text{ mg/m}^2/\text{cycle}$ , (administered initially as  $10 \text{ mg/m}^2/\text{day} \times 10$  days per cycle, and subsequently as  $20 \text{ mg/m}^2/\text{day} \times 5$  days per cycle) combined with GM-CSF, plus 13-cis-retinoic acid, the 56 patients treated in CR/VGPR after conventional therapy achieved 70% two-year RFS. By taking into account of the small sample variation, we will consider a two-year RFS rate 0.64 as not promising and 0.80 as promising with the new treatment. Twenty-two patients will be accrued initially, and if there are less than 15 RFSs, further accrual to the protocol will be stopped and the new treatment will be declared ineffective in this protocol. If there are at least 15 RFSs, then an additional 36 patients will be accrued for a total of 58. If at least 42 RFSs out of 58 patients, the protocol would be considered to have a positive result and the new treatment would be considered worthy of further testing in this patient population. The probability of stopping the study earlier is 57% under the null hypothesis.

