### 14.4 Secondary Endpoint

The association between histologic examination and real time RT-PCR regarding BM status will be assessed by the Wilcoxon statistic. The clinical significance (relapse-free survival) of histologic results and real time RT-PCR findings will be assessed by log-rank test and Cox regression model.

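### Does the promised comparison with the predecessor trials need a defined comparator and method, and would GM-CSF route pass for a dose effect?

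*Combined protocol and SAP*

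**What the plan says.** The primary objective in section 2.0 is "Assess the impact of high-dose 3F8/GM-CSF on relapse-free survival in patients in first complete or very good partial remission". Section 4.1 describes an open-label, single-arm trial and adds "Clinical results will be compared to those in the predecessor trials which used only the standard 3F8 dosage".

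Section 14.2 supplies a benchmark. On IRB 03-077, at standard dosage, "the 56 patients treated in CR/VGPR after conventional therapy achieved 70% two-year RFS". Allowing for sampling variation in that figure, it calls 0.64 not promising and 0.80 promising, then states a Simon two-stage rule: stop with fewer than 15 successes among 22 patients, otherwise go to 58 and call the result positive at 42 or more. A positive result means only that the treatment merits further testing.

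Section 14.4 covers the marrow findings: "The clinical significance (relapse-free survival) of histologic results and real time RT-PCR findings will be assessed by log-rank test and Cox regression model". It does not mention predecessor trials.

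On GM-CSF route, section 3.5 lists among the results of earlier 3F8/GM-CSF studies "the superiority of subcutaneous over intravenous (iv) use of GM-CSF, for both anti-NB effect and treatment simplification". Section 3.8 gives the recent findings this trial draws on as "namely, high dosing of 3F8 and subcutaneous use of GM-CSF". Section 9.1 says GM-CSF dosing follows the predecessor protocols. No section gives the route used in the 56 patients.

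**The concern.** With one arm, any statement about high against standard dose has to come from outside the trial. Section 4.1 promises such a comparison, but nothing in section 14 says which trials enter it, how the difference is estimated or what is adjusted for. Section 4.1 speaks of trials in the plural, section 3.5 cites both 94-018 and 03-077, and section 14.2 uses 03-077 alone. In principle the comparator could be picked once results are known.

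Route looks like a second problem. The protocol holds that subcutaneous GM-CSF is the more active route and names it beside the higher 3F8 dose. If part of the comparator had intravenous GM-CSF, a raw difference in RFS would mix route with dose. At stake would be a claim that high dose beats standard dose, resting on a comparison chosen afterwards and confounded by a factor the protocol itself considers active.

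**Working it through.** **1. The plan's own figures.** Inputs from section 14.2: n1 = 22, continue at 15 or more, N = 58, positive at 42 or more, p0 = 0.64, p1 = 0.80.

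- Early stopping = P(X1 ≤ 14 | 22, p). At 0.64 this is 0.5656; the plan states 57%.
- P(positive) = Σ over x1 = 15 to 22 of P(X1 = x1) × P(X2 ≥ 42 − x1 | 36, p). At 0.64 this is 0.0990 (limit 0.1). At 0.80 it is 0.9056, so the type II error is 0.0944 (limit 0.1).

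The rule is correct as stated.

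**2. Does section 14.2 already meet the standard-dose experience?** Treating 70% as a simple proportion of 56, SE = √(0.70 × 0.30 / 56) = 0.0612, and 0.70 − 0.0612 = 0.639. The null of 0.64 is therefore the 03-077 rate less one standard error. Trial, cohort, endpoint and decision method are all named for the primary analysis.

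**3. Which trials?** Sections 3.7, 10.7 and 14.2 each identify the predecessor as 03-077. Section 3.5 cites 94-018 and 03-077 for activity against refractory marrow disease, whereas this trial enrols patients in first CR/VGPR (section 6.1.3). It does not offer them there as RFS comparators. What remains open is the plural in section 4.1, echoed in section 9.1.

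**4. How much could the comparison show?** Assume 56 predecessor patients at 70% and n high-dose patients. The documents do not give the number enrolled by A(7), so a range is shown. Half-width of the 95% interval at equal rates = 1.96 × √(0.21/n + 0.21/56).

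| n | Half-width |
|---|---|
| 58 | 16.8 points |
| 40 | 18.6 points |
| 22 | 22.6 points |

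A result exactly at the success bar is 42/58 = 72.4%, or 2.4 points above 70%. Its standard error is √(0.724 × 0.276/58 + 0.21/56) = 0.085, giving an interval of about −14 to +19 points. For illustration only, since no two-sample test is planned, power to separate 0.80 (n = 58) from 0.70 (n = 56) is about 0.23 at two-sided 0.05 and 0.48 at one-sided 0.10.

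**5. Route.** If a share f of the comparator had intravenous GM-CSF and route is worth d points of two-year RFS, the spurious difference is f × d. The documents give neither value. Assumed pairs yield 0.25 × 5 = 1.25, 0.50 × 10 = 5 and 0.75 × 15 = 11.25 points, and zero if all were treated subcutaneously. Section 3.5 credits the route finding to studies that came before this trial, so some earlier patients may have had intravenous GM-CSF, but subcutaneous use also predates this protocol. The references attached to that statement are, by their titles, about pharmacokinetics and neutrophil migration, so they do not anchor d.

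**6. The comparator difference that is documented.** Section 14.2 says the 03-077 schedule moved from 10 mg/m²/day × 10 days to 20 mg/m²/day × 5 days. Both total 100 mg/m² per cycle, against 80 × 5 = 400 mg/m² in the high-dose cycles here. Any account of the comparator would mention this, and the protocol already discloses it.

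**The case for a change.** The best case for a change is that section 14.2 asks whether RFS exceeds 0.64, not whether it exceeds the 70% seen at standard dose. If the true rate were 70%, no better than the predecessor, the rule would still be positive with probability 0.36, or 0.41 if the stage 1 stop were not enforced. A positive trial thus says little about dose, and the only text that speaks to dose directly is the undefined sentence in section 4.1. One paragraph would fix the comparator and label the comparison descriptive, with no extra patients.

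The gap in the text is real, the plural is unresolved, and the route in the 56 patients should be known before anyone interprets a difference. But the 0.36 describes a screening rule whose claim is limited to further testing; it is not an error in the comparison. The pieces a careful analyst needs are already in place: high-dose treatment is confined to patients enrolled on A(0) to A(7) (section 4.2), later patients count only toward toxicity (section 14.0), and response duration runs from the first day of 3F8 (section 12.1). A Cox model with chosen covariates, or a disclaimer against a superiority claim the plan never makes, would be a matter of preference. High-dose treatment of new patients also ended at A(8), so whether new text at A(10) could still precede the results is unknown.

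**Conclusion.** No change to the plan. The primary decision rule, its null and its error rates are right and do not depend on the section 4.1 comparison. That comparison is secondary and descriptive. Section 14.2 already identifies its natural comparator, and its precision, 17 points either way at best, rules out a firm reading about dose whichever way it is reported. A route difference is possible but not shown: its illustrated size runs from 0 to 11 points on assumed inputs, and it is settled by asking the sponsor how the 56 patients received GM-CSF. An analyst would report two-year RFS with intervals for the A(0) to A(7) patients and the 03-077 cohort, and state that cohort's 3F8 schedule and GM-CSF route.

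This rests on treating 70% as a simple proportion of 56, since no count or interval is given, and on the comparison staying descriptive. If a report used it to claim superiority over standard dose, the objection would apply to that report.
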